Development of a standardized myofascial examination protocol. Pelvic floor myofascial pain can be a challenging condition to treat, but more importantly, it is often not diagnosed. Unfortunately, until recently, a consistent and validated examination technique that reliably identifies pelvic floor myofascial pain has not yet been published (29). We recently completed a systematic review that found limited consensus on methods to assess pelvic floor myofascial pain (30). To address this lack of standardization, our team developed a standardized pelvic floor myofascial examination protocol in collaboration with Washington University Women's Health PT faculty. An iterative process was used to standardize the examination. Four physicians performed an initial examination on a simulated patient from the Washington University Standardized Patient Program who provided specific, real-time feedback on location, pressure, and technique of palpation among the examiners. The physicians repeated the examination until consensus was achieved. A force sensor was then used to formally standardize pressure between examiners. This examination protocol has been

implemented in our clinics by all providers, and has been shown to have high correlation between examiners (29).

C Study Objectives

C1 Specific Aims

Specific Aim 1: To determine the effect of vaginal cryotherapy as an immediate treatment modality for patients with pelvic floor myofascial pain.

Hypothesis 1: Vaginal cryotherapy will result in a significant immediate improvement in pelvic floor myofascial pain compared to placebo.

Specific Aim 2: To determine the effect of vaginal cryotherapy as a neoadjuvant treatment modality for patients with pelvic floor myofascial pain awaiting pelvic floor PT.

Hypothesis 2A: Vaginal cryotherapy will result in a significant improvement in pelvic floor myofascial pain compared to placebo.

D Investigational Agent

D1 Clinical Data to Date

Cryotherapy is a well-known and effective adjunct treatment modality for acute and chronic musculoskeletal injuries. Through tissue cooling, cryotherapy decreases tissue metabolism and reduces blood flow to injured tissue, which results in diminished inflammation and edema, ultimately leading to reduced muscle spasm and pain (7). Neural conductance velocity is also slowed, which further contributes to pain reduction (21).

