This is a placebo-controlled, randomized controlled trial to investigate the role of vaginal cryotherapy on pelvic floor myofascial pain in women. This study involves randomizing patients who are found to have pelvic floor myofascial pain on examination into one of two treatment groups: transvaginal cryotherapy or transvaginal application of a room-temperature tube. Patients will be followed up at two different time points in order to assess response to treatment. Follow-up times include immediately after application (Specific Aim #1) and two weeks following use of the intervention alone (Specific Aim #2). Patients will be referred to pelvic floor PT, which is considered the standard of care for treatment of pelvic floor myofascial pain at this time. As it typically takes 2-3 weeks to get in to see one of the pelvic floor PT providers at Wash U, follow up for this study will be completed prior to their attendance at pelvic floor PT.

E2 Subject Selection and Withdrawal

2.a Inclusion Criteria

Study population and eligibility: All new patients presenting to our facility undergo our standardized pelvic floor myofascial examination and are asked to rate their pain on palpation of the bilateral OI and LA muscles on a 0-10 verbal pain rating scale (0=none 1-3=mild, 4-6=moderate, and 7-10=severe). Patients found to have pelvic floor myofascial pain of at least 4/10 in severity at any of the four sites will be eligible for inclusion. Eligible patients may participate in Specific Aim 1 only or in both Specific Aims 1 and 2.

2.a Exclusion Criteria

Exclusion criteria include age <18, non-English speaking, current diagnosis of dementia, and limited physical mobility that would prevent full participation in pelvic floor PT. Patients will also be excluded if they have performed vaginal cryotherapy in the past or present with a complaint or known history of chronic pelvic pain.

2.b Ethical Considerations

Human Subjects Involvement and Characteristics

We will approach adult women presenting to the FPMRS Clinic at Washington University in St. Louis for inclusion. Eligible women will be ≥ 18 years old, English speaking, found to have pelvic floor myofascial pain on examination, and willing to participate.

Inclusion of Women, Minorities, and Children

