Patients participating in Specific Aim #1 will insert this tube into the vagina to a comfortable depth. A lubricant will be provided for comfort with tube insertion, if necessary. At the conclusion of the treatment, this tube will be washed thoroughly and given to the patient in a clean plastic baggie for use at home.

Patients in Specific Aim #2 will also be given two tubes according to the group to which they were randomized for use at home.

3.b Treatment Regimen

Both groups will be given the same instructions for use, which will include intravaginal placement of one tube for 10 minutes while resting in a supine position. A lubricant may be used for comfort with insertion.

Patients participating in Specific Aim #1 will perform their first intervention in the office with a repeat examination within 10 minutes of completing therapy. Patients participating in Specific Aims #2 will perform the intervention once daily at home. Patients will be asked to complete a short diary for each session, which will include the time of day, duration of application, pain score prior to and after application, and presence of any pelvic floor disorder symptoms prior to and after application.

3.c Method for Assigning Subjects to Treatment Groups

Randomization will be in 1:1 allocation to either vaginal cryotherapy or control. The examining physician and study PI will be blinded to treatment allocation. The research assistant will be aware of study allocation in order to provide instruction and answer questions but will not be involved in data collection or analysis.

3.d Preparation and Administration of Study Intervention

Cryotherapy and control tubes will be prepared by the investigators and stored on-site until randomization and treatment allocation. The tubes used for the cryotherapy and control interventions are identical, 10 ml conical tubes. Cryotherapy tubes (intervention arm) will be prepared using a mixture of isopropyl alcohol (2ml) and water (8ml) and stored in the freezer. Using this mixture results in a “slushy” consistency and prevents the contents of the tube from freezing solid, thus decreasing the risk of tissue injury. Control tubes will be empty and stored at room temperature.

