Grade IV	Life-threatening complication (including CNS complications)* requiring IC/ICU management
Grade IVa	Single organ dysfunction (including dialysis)
Grade IVb	Multiorgan dysfunction
Grade V	Death of a patient
Suffix "d"	If the patient suffers from a complication at the time of discharge (see examples in Table 2), the suffix "d" (for "disability") is added to the respective grade of complication. This label indicates the need for a follow-up to fully evaluate the complication.

*Brain hemorrhage, ischemic stroke, subarachnoidal bleeding, but excluding transient ischemic attacks.
CNS, central nervous system; IC, intermediate care; ICU, intensive care unit.

F4 Study Outcome Measurements and Ascertainment

The data collected will include demographic characteristics; basic medical and reproductive health histories; pre- and post-treatment myofascial examination scores; PFDI-20, PFIQ-7, and PISQ-IR results at baseline and follow up visits; PGI-I and SAPS scores at study conclusion; PFPT assessments. Demographic data, medical and reproductive health histories, and pre- and post-treatment myofascial examination scores will be obtained from the medical record. Baseline questionnaires will be completed by the patient electronically directly in REDCap using a secure, password-protected tablet owned and operated by the research team. Follow up surveys and questionnaires will be administered electronically as secure surveys built in REDCap.

G Statistical Plan

G1 Sample Size Determination and Power

We expect vaginal cryotherapy to result in at least 3-point improvement in myofascial pain scores as reported on a 0-10 verbal pain rating scale. Prior studies investigating clinically significant reductions in pain scores report greater than 2 points on a 0-10 scale or 30% reduction in pain as clinically significant²⁸. In order to detect a 3-point difference with 80% power and alpha 0.05, we would need to enroll 30 patients per group. Accounting for a 20% loss-to-follow up rate, we plan to enroll 33 patients per group for a total of 66 patients. Patients may participate in Specific Aim #1 only, in Specific Aim #2 only, or both Specific Aims. If no patients participate in both Specific Aim #1 and Specific Aim #2, then 132 patients will be required overall.

G2 Interim Monitoring and Early Stopping

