This study is designed as a pilot study to test the efficacy and feasibility of vaginal cryotherapy for treatment of pelvic floor myofascial pain. As such, we do not have futility criteria for early stopping. We will monitor for adverse events and pause/stop enrollment for this as indicated above.

G3 Analysis Plan

Specific Aim #1: To determine the effect of vaginal cryotherapy as an immediate treatment modality for patients with pelvic floor myofascial pain. Primary outcome is change in pelvic floor myofascial pain scores at each site (bilateral OI and LA). The statistical significance of this change between arms will be evaluated by a Students t-test or Wilcoxon rank sum test as appropriate. Secondary outcomes include change in PFDI-20, PFIQ-7, and PISQ-IR scores.

Specific Aim #2: To determine the effect of vaginal cryotherapy as a neoadjuvant treatment modality for patients with pelvic floor myofascial pain awaiting pelvic floor PT. Primary outcome includes change in pelvic floor myofascial pain scores at each site (bilateral OI and LA) from baseline to follow-up (2 weeks). The statistical significance of this change between arms will be evaluated by a Students t-test or Wilcoxon rank sum test as appropriate. Secondary outcomes include change in PFDI-20, PFIQ-7, and PISQ-IR scores, and patient satisfaction (PGI-I, SAPS).

G4 Missing Outcome Data

Patients with missing outcome data for the primary outcome will be excluded from analysis. The primary analysis will be by intention-to-treat with a planned secondary analysis per-protocol. Missing outcome data for secondary outcomes of PFDI-20, PFIQ-7, and PISQ-IR scores will be imputed according to published protocols for imputation of missing data within these questionnaires (26, 27).

H Data Handling and Record Keeping

H1 Confidentiality and Security

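### Each aim has four site-level primary outcomes but one hypothesis, and no rule links them, so the success criterion is undefined

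*Combined protocol and SAP*

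**What the plan says.** Section G3, Aim 1: "Primary outcome is change in pelvic floor myofascial pain scores at each site (bilateral OI and LA". For Aim 2: "Primary outcome includes change in pelvic floor myofascial pain scores at each site (bilateral OI and LA) from baseline to follow-up (2 weeks". Both aims use a t-test or Wilcoxon test between arms. Section E2 2.a confirms that there are four sites, since entry requires "pelvic floor myofascial pain of at least 4/10 in severity at any of the four sites will be eligible for inclusion".

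Section C1 gives one hypothesis per aim. Hypothesis 1: "Vaginal cryotherapy will result in a significant immediate improvement in pelvic floor myofascial pain compared to placebo". Hypothesis 2A: "Vaginal cryotherapy will result in a significant improvement in pelvic floor myofascial pain compared to placebo". Neither names a site, and the overall hypothesis in A2 is equally general.

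Section G1 gives one power statement: "In order to detect a 3-point difference with 80% power and alpha 0.05, we would need to enroll 30 patients per group". It does not say whether the 3 points apply to one site, every site or a summary score. The document contains no composite score, index site, testing order, multiplicity adjustment or required number of significant sites.

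**The concern.** Suppose two of the four sites reach p < 0.05 in Aim 1. The plan does not say whether Hypothesis 1 is then supported. One reader could report success and another failure from the same data, each consistently with G3. A rule chosen once the site results are known does not give a test with a known error rate.

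The gap also detaches G1 from G3. The 80% power belongs to a single comparison, and G3 has no single comparison. Because entry needs 4/10 at only one site, some sites may start with little pain and have little room to improve. The documents do not allow the size of that effect to be worked out.

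**Working it through.** **Inputs.** From G1: difference 3 points, power 80%, alpha 0.05 (sidedness not stated; two-sided assumed), 30 per group. From E2 and G3: four sites. Assumed: each site tested at 0.05, and equal correlation between sites, shown over a range.

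**1. The plan's own figure.** The 30 per group cannot be reproduced because G1 gives no SD. Solving backwards with the normal approximation, SD = 3 / [(1.960 + 0.842) × √(2/30)] = 4.15. With the t distribution, the standardised difference is 0.7356 and SD = 3 / 0.7356 = 4.08. A one-sided test would imply 4.67.

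**2. False-positive rate per aim with no true effect.** With independent sites, any site significant in either direction: 1 − 0.95⁴ = 18.5%. Counting only results favouring cryotherapy: 1 − 0.975⁴ = 9.6%, against a nominal 2.5%. With correlated sites, by simulation:

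| Correlation | Any site, either direction | Any site, favouring cryotherapy | At least two sites | All four |
|---|---|---|---|---|
| 0 | 18.5% | 9.6% | 1.4% | 0.0% |
| 0.5 | 15.6% | 7.8% | 3.3% | 0.1% |
| 0.7 | 13.0% | 6.5% | 4.7% | 0.6% |
| 0.9 | 9.4% | 4.7% | 5.3% | 1.9% |
| 0.95 | 8.0% | 4.0% | 5.4% | 2.7% |

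The two-site and all-four columns count either direction. Requiring at least three sites gave at most 3.9% over this range. Repeat runs moved these figures by about 0.3 points at most.

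**3. Power if all four sites must be significant.** This assumes a true 3-point effect at every site.

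| SD | Per group | Correlation 0 | 0.5 | 0.7 | 0.9 |
|---|---|---|---|---|---|
| 4.08 | 30 | 41% | 55% | 62% | 70% |
| 4.08 | 26 | 30% | 46% | 53% | 62% |
| 4.08 | 33 | 49% | 62% | 67% | 75% |
| 3 | 30 | 88% | 90% | 92% | 94% |
| 3 | 26 | 79% | 84% | 86% | 90% |

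The 26 comes from G1's recruitment statement, "Accounting for a 20% loss-to-follow up rate, we plan to enroll 33 patients per group for a total of 66 patients": 33 × 0.8 = 26.4. The 33 may be nearer the mark for Aim 1, which has a "repeat examination within 10 minutes of completing therapy".

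At SD 4.08, 30 per group and correlation 0.5, unadjusted power is about 90% for at least two sites and 78% for at least three. Power therefore varies widely with a rule that is not written down.

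**The case against.** The strongest reply is that the plan never adopts the any-site rule, which is the only one of these rules with material inflation. Requiring two sites roughly holds 5%, and requiring three or four holds it fully. All four scores come from one patient in one standardised examination, so independence is implausible. The hypotheses are directional, so a site favouring control would not support them. All of this stands. A reader might infer that the trial carries an 18.5% false-positive rate; the documents do not support that, because the figure needs both independent sites and a rule the plan does not contain.

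A reader might also infer that the trial is underpowered. That does not follow either. The SD of 4.08 is back-calculated, and at an SD of 3 even the all-four rule has 88% to 94% power at 30 per group. The simulations also use normal outcomes, whereas the scale is a bounded 0–10 score and G3 allows a Wilcoxon test.

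A third reply is that this is a single-centre pilot and that reporting all four p-values would let readers judge for themselves. The pilot label does not settle the matter. G2 uses it to explain the absence of futility criteria, and the same section says the trial tests efficacy. The hypotheses are stated in terms of significance, and G1 powers the trial at alpha 0.05. Reporting four p-values shows the multiplicity but still does not say whether the hypothesis was supported.

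**Conclusion.** The concern holds as an undefined success criterion in both aims. It is not a demonstrated error rate. If any site counts, the two-sided rate per aim is about 9.5% to 15.5% at correlations of 0.9 to 0.5, bounded by 18.5%; for results favouring cryotherapy it is about 4.7% to 7.8%, bounded by 9.6%, against 2.5%. If two sites are needed, it is at most about 5.4%; if three or four, there is no inflation. If all four are needed, power at 30 per group is about 41% to 70% instead of 80%, given an SD of 4.08, a two-sided test and a 3-point effect at every site. G1's 80% is tied to no outcome in G3.

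The error rates rest on assumed correlations and a per-site alpha of 0.05; the power figures also rest on the back-calculated SD. The missing rule itself rests on no assumption. It affects the main conclusion of each aim, so it must be corrected before outcome data are seen.

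**What to change.** In G3, define one primary pain score for each aim. Suggested wording: *The primary outcome is the change in the average of the four site scores (left and right OI, left and right LA), compared between arms at a two-sided 0.05 level.* An alternative is the change at an index site, meaning the site with the highest baseline score, with ties broken by a fixed site order. Make the four individual sites secondary, with Holm adjustment. Restate G1's power for the chosen score, with its assumed SD.

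No new data are needed, because F4 already collects examination scores before and after treatment. The costs are:

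- Claims about individual sites become secondary, and the question is no longer about each site.
- A mean includes sites with little pain, which can dilute the effect. As an illustration at SD 4.08 and correlation 0.5, the SD of the mean is 4.08 × √[(1 + 3 × 0.5)/4] = 3.23, and its standard error with 30 per group is 3.23 × √(2/30) = 0.833. A 3-point effect at every site gives 3/0.833 − 1.96 = 1.64, or about 95% power. Three points at two sites and none at the others averages 1.5 points: 1.5/0.833 − 1.96 = −0.16, or about 44%.
- The restated power may therefore be less favourable than 80%.

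Keeping four primary outcomes is acceptable only if G3 states how many sites must be significant in favour of cryotherapy and G1 gives power for that number. If that number is one, Holm adjustment would be needed. At SD 4.08 and 30 per group it would lower any-site power from 97% to 88%, 94% to 82% and 89% to 74% at correlations of 0.5, 0.7 and 0.9.

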Our patient sample is limited to women. St. Louis City is approximately 50% Black or African American, but our surrounding suburbs and rural areas have a much lower proportion of residents who are African American. We will strive for at least 25% racial/ethnic minority representation in our study (25% African Americans, 1% Asian American, 1% American Indian/Alaska Native). There are no exclusion criteria in this application related to race/ethnicity, however, we will exclude non-English speaking individuals. We do not anticipate this negatively affecting the racial/ethnic minority representation in our study as the proportion of individuals who do not speak English in the St. Louis region is low. We will not include children <18 in our study.

2.c Subject Recruitment Plans and Consent Process

A member of the research team will approach eligible patients and further describe the study. Confidential and informed consent will occur in a private room. Patients will receive verbal and written instructions on using the intravaginal tubes by the research assistant who will not be blinded to treatment allocation. Providers performing the baseline and follow-up pelvic floor myofascial examination and interpreting the data will be blinded to treatment allocation.

2.d Randomization Method and Blinding

Randomization will be in 1:1 allocation to either vaginal cryotherapy or control. The examining physician and study PI will be blinded to treatment allocation. The research assistant will be aware of study allocation in order to provide instruction and answer questions but will not be involved in data collection or analysis.

2.e Risks and Benefits

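### The primary comparison of change scores makes no covariate adjustment for the site's baseline pain score, which is already collected; a baseline-adjusted linear model may narrow the interval at little cost

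*Combined protocol and SAP*

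**What the plan says.** Section G3 (Analysis Plan) defines the primary outcome of each aim as change in the myofascial pain score at each site, that is, the obturator internus and levator ani on both sides. Aim 1 looks at the immediate change and Aim 2 at the change from baseline to 2 weeks. The same sentence governs both: "The statistical significance of this change between arms will be evaluated by a Students t-test or Wilcoxon rank sum test as appropriate". Neither G3 nor any other section names a covariate, a regression model or ANCOVA.

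The baseline score at each site is available. Section F4 lists it among the study data: "pre- and post-treatment myofascial examination scores will be obtained from the medical record". It is also the eligibility measurement. Under section E2, patients with "pelvic floor myofascial pain of at least 4/10 in severity at any of the four sites will be eligible for inclusion", so a patient can qualify on one site and have a low score, even 0, at another site where she is also analysed.

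On design, section E2 2.d states: "Randomization will be in 1:1 allocation to either vaginal cryotherapy or control". Section G1 states: "Accounting for a 20% loss-to-follow up rate, we plan to enroll 33 patients per group for a total of 66 patients".

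**The concern.** A change score does use the baseline, but it subtracts the whole of it: the baseline weight is set at 1 whatever the data show. ANCOVA estimates the weight. If baseline and follow-up are only moderately correlated, subtracting the full baseline adds noise that the model would remove. The entry rule makes this relevant here, because baselines at a given site can be spread over most of the 0-10 scale and are likely to predict how much a patient can change.

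At stake is precision. With 33 patients per arm at most, and fewer after loss, the interval for the treatment difference may be wider than the collected data require.

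**Working it through.** **The plan's own figure.** Section G1 says: "In order to detect a 3-point difference with 80% power and alpha 0.05, we would need to enroll 30 patients per group". It gives no standard deviation (SD), so the 30 cannot be reproduced forward. That does not affect this check, because the ratio below does not depend on the absolute SD. For the number evaluable I take the planned 33 per arm less the stated 20% loss: 33 × 0.8 = 26.4, taken as 26. (Whether 33 follows from 30 with 20% loss is a separate matter.)

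**Inputs from the documents.** 1:1 allocation (E2 2.d); t-test or rank-sum test on change (G3); 33 per arm and 20% loss (G1).

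**Assumed inputs.** ρ, the baseline to follow-up correlation at a site, and k, baseline SD divided by follow-up SD. The documents give neither. Both are taken as common to the two arms.

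**Formula.** With σ the follow-up SD, the variance of the treatment difference is proportional to:
- change score: σ²(1 + k² − 2ρk)
- ANCOVA: σ²(1 − ρ²)

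The first bracket minus the second is (k − ρ)², which is never negative. Hence the large-sample ordering, with equality only when ρ = k. The ratio is (1 − ρ²)/(1 + k² − 2ρk).

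**Cost of estimating the slope.** With n per arm this is about 1 + 1/(2n − 4). At n = 26 it is 1 + 1/48 = 1.021.

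| k | ρ | Ratio | Ratio × 1.021 |
|---|---|---|---|
| 1 | 0.3 | 0.91/1.40 = 0.65 | 0.66 |
| 1 | 0.5 | 0.75/1.00 = 0.75 | 0.77 |
| 1 | 0.7 | 0.51/0.60 = 0.85 | 0.87 |
| 1 | 0.9 | 0.19/0.20 = 0.95 | 0.97 |
| 0.8 | 0.5 | 0.75/0.84 = 0.89 | 0.91 |
| 0.8 | 0.7 | 0.51/0.52 = 0.98 | 1.00 |
| 0.7 | 0.7 | 0.51/0.51 = 1.00 | 1.02 |

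These are illustrations, not bounds. A k above 1 can give a larger gain: k = 1.25 with ρ = 0.3 gives 0.91/1.8125 = 0.50.

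**What this means for the interval.** Width scales with the square root of the variance. At k = 1 and ρ = 0.5, √0.766 = 0.875, so the interval is about 12% narrower. If the SD of change were 2 points (an assumption), the 95% CI half-width at 26 per arm would go from 1.11 to 0.98 points.

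**Bounded scores.** The formula ignores rounding, the 0-10 limits and selection on any of four sites. A simulation with all three, at 30 per arm and with an assumed true effect of 0 or 1.5 points, gave ratios of about 0.68-0.70, 0.73-0.79, 0.84-0.88 and 0.94-0.96 at ρ = 0.3, 0.5, 0.7 and 0.9. Type I error was near 5% for both methods and their mean estimates agreed.

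**The case against.** The strongest reply is that this is a preference and not a defect. The planned test is unbiased under randomisation and holds its type I error, and section G2 describes the trial as a pilot. That stands, and it limits the point to a suggested improvement.

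A second reply is that the gain is unproven, since neither ρ nor k is known. That also stands. At k = 0.8 and ρ = 0.7 the slope cost uses up the whole gain, and at ρ = k about 2% is lost.

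A third is that G3 also allows the rank-sum test, which may be the branch used at sites with many baseline scores near 0. No loss has been shown for that branch, and a linear baseline term would not remove the floor effect there.

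Two stronger readings are tempting:
- A reader might infer that the plan loses a definite amount of power. That would need the SD of change, which G1 does not state. Solving backwards from 30 per group gives about 4.08, which sits badly with a 0-10 scale: at k = 1 and ρ = 0.7 it implies a baseline SD of 4.08/√0.6 = 5.26, when the maximum possible is about 5. At a change SD of 2, power for 3 points at 26 per arm exceeds 99% either way.
- A reader might infer that chance baseline differences between arms would bias the unadjusted result. The unadjusted standard error already allows for them, so they are not a second cost.

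**Conclusion.** The point holds as a conditional gain in precision. G3 leaves the collected baseline out as a covariate, and the t-test on change is in large samples never more precise than ANCOVA under 1:1 allocation. Before the slope cost, variance falls by about 35%, 25%, 15% and 5% at k = 1 and ρ = 0.3, 0.5, 0.7 and 0.9, by about 11% and 2% at k = 0.8 and ρ = 0.5 and 0.7, and not at all at ρ = k. All of this rests on assumed ρ and k, common to both arms.

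The documents do not support calling the planned analysis invalid, claiming a particular power gain, or claiming a loss for the rank-sum branch. How G4 handles missing primary scores is a different question, and nothing here bears on it. This is a change worth considering, not a correction that the trial depends on.

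**What to change.** In G3, for each aim and each site, make the primary analysis a linear model of the follow-up score on treatment arm with that site's baseline score as covariate. Report the adjusted difference between arms with its 95% CI. Keep the rank-sum test on change as a sensitivity analysis, which also gives a check where scores are skewed or bunched near 0. Specify this before outcome data are seen, so that adjusted and unadjusted results are not chosen between afterwards.

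The cost is a few lines of plan text and analysis code, with no new data. The downside is about 2% of variance at 26 per arm if ρ turns out close to k. The linear baseline term does not cure a floor effect at sites that start near 0.
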